6.11.1. Primary Outcome and Methodology

The validated Investigator's Global Assessment for AD (IGA) uses the clinical characteristics of erythema, papulation/induration, oozing/crusting and lichenification to produce a single-item score ranging from 0 to 4. The primary analysis of the study is to test the null hypotheses that neither baricitinib 4-mg nor baricitinib 2-mg is superior to placebo when evaluating the proportion of patients achieving IGA of 0 or 1 at Week 16 in the ITT population. The analysis assumes that treatment response disappears after patients are rescued or permanently discontinued from treatment. This will serve as the primary estimand. In this estimand, missing data due to the application of the primary censoring rule and the occurrence of other non-censor intercurrent events will be imputed using the NRI method described in Section 6.4.1.

A supplemental estimand is to test the null hypotheses that neither baricitinib 4-mg nor baricitinib 2-mg is superior to placebo when evaluating the proportion of patients achieving IGA of 0 or 1 at Week 16 in the ITT population. This analysis assumes the treatment response disappears after patients permanently discontinued from treatment. In this supplemental estimand, missing data due to the application of the secondary censoring rule and the occurrence of other non-censor intercurrent events will be imputed using the NRI method described in Section 6.4.1.

A logistic regression analysis as described in Section 6.2.3 will be used for the comparisons. The odds ratio, the corresponding 95% CIs and p-value, as well as the treatment differences and the corresponding 95% CIs, will be reported.

Multiplicity controlled analyses will be performed on the primary and key secondary (see Section 4.2.1) objectives to control the overall Type I error rate at a 2-sided alpha level of 0.05. A graphical approach will be used to perform the multiplicity controlled analyses as described in Section 6.6.

6.11.2. Secondary and Exploratory Efficacy Analyses

For secondary analysis, the null hypotheses is that neither baricitinib 4-mg nor baricitinib 2-mg is superior to placebo in the ITT population. These analyses assume treatment response disappears after patients are rescued or permanently discontinued from treatment and will serve as the primary estimand. In this estimand, missing data due to the application of the primary censoring rule and the occurrence of other non-censor intercurrent events will be imputed using the method described in Table JAHM.6.1.

A supplemental estimand for secondary endpoints is to test the null hypotheses that neither baricitinib 4-mg nor baricitinib 2-mg is superior to placebo in the ITT population. These analyses assumes the treatment response disappears after patients permanently discontinued from treatment. In this supplemental estimand, missing data due to the application of the secondary censoring rule and the occurrence of other non-censor intercurrent events will be imputed using the method described in Table JAHM.6.1.

A list of exploratory endpoints are provided in Section 4.2.2. There will be no adjustment for multiple comparisons for exploratory endpoints. The secondary and exploratory efficacy endpoints are detailed in Table JAHM.6.4 and analyses are provided in Table JAHM.6.5. Health outcomes analyses are described in Section 6.12.

6.11.3. Sensitivity Analyses

Sensitivity analyses are included to demonstrate robustness of analyses methods using different missing data imputations, censoring rules, populations and analyses assumptions. Sensitivity analyses for select outcomes have been previously described and include the following:

- Analyses of key endpoints using the per-protocol analysis set (Section 6.2.1)
- Analyses of key endpoints using the secondary censoring rule (Section 6.2)
- Placebo multiple imputation (Section 6.4.4)
- Tipping point analysis (Section 6.4.5)
- The addition of a treatment-by-region interaction to the logistic regression model for the primary outcome (Section 6.5)
- Analysis of continuous outcomes with ANCOVA (Section 6.2.3), with missing data imputed using mLOCF (Section 6.4.3).

6.12. Health Outcomes/Quality-of-Life Analyses

The general methods used to summarize health outcomes and quality-of-life measures, including the definition of baseline value for assessments are described in Section 6.1.

Health outcomes and quality-of-life measures will generally be analyzed according to the formats discussed in Section 6.11.

Table JAHM.6.6 includes the descriptions and derivations of the health outcomes and quality-of-life measures.

Table JAHM.6.7 provides the detailed analyses including analysis type, method and imputation, population, time point, and comparisons for health outcomes and quality-of-life measures.

Additional psychometric analyses will be performed by Global Patient Outcomes Real World Evidence at Lilly and documented in a separate analysis plan.

Table JAHM.6.6. Description and Derivation of Health Outcomes and Quality-of-Life Measures

Measure	Description	Variable	Derivation / Comment	Imputation Approach if Missing Components
Itch Numeric Rating Scale (NRS)	The Itch Numeric Rating Scale (NRS) is a patient-administered, 11-point horizontal scale anchored at 0 and 10, with 0 representing “no itch” and 10 representing “worst itch imaginable.” Overall severity of a patient’s itching is indicated by selecting the number that best describes the worst level of itching in the past 24 hours (Naegeli et al. 2015; Kimball et al. 2016). Refer to Section 6.2.2 for details on how to calculate the weekly score which will be used in the continuous analysis.	Itch NRS score	Single item; range 0-10. Refer to Section 6.2.2 on how to derive the visit score.	Refer to Section 6.2.2 on how to derive the weekly visit score.
		
 ▪ Change from baseline in Itch NRS ▪ Percent change from baseline in Itch NRS 	Change from baseline: observed Itch score – baseline Itch score % change from baseline: $100 \times \frac{\text{Observed score} - \text{Baseline}}{\text{Baseline}}$	Missing if baseline or observed value is missing.
		4-point Itch improvement in subgroup of patients with baseline Itch NRS ≥ 4	Change from baseline ≤ -4 and baseline ≥ 4	Missing if baseline is missing or <4 or observed value is missing.
		Itch-free days (Itch NRS = 0)	Count of observed value = 0 for 28-day (4-week) intervals starting on the day of the first study drug administration. This will be calculated for the following visit intervals: baseline to Week 4, Week 4 to Week 8, Week 8 to Week 12 and Week 12 to Week 16. Day 1 is defined as the day of first study drug administration therefore the baseline to Week 4 assessment is based on Day 1 to Day 28, Week 4 to Week 8 is based on Day 29 to Day 56, etc.	If patients do not have at least 16 non-missing assessments in each 4-week interval, the score is missing.
Skin Pain Numeric Rating Scale (NRS)	Skin Pain NRS is a patient-administered, 11-point horizontal scale anchored at 0 and 10, with 0 representing “no pain” and 10 representing “worst pain imaginable.” Overall severity of a patient’s skin pain is indicated by selecting the number that best describes the worst level of skin pain in the	Skin Pain NRS score	Single item; range 0 to 10. Refer to Section 6.2.2 on how to derive the visit score.	Refer to Section 6.2.2 on how to derive the visit score.
		Change from baseline in Skin Pain NRS	Change from baseline: observed skin pain score – baseline skin pain score	Missing if baseline or observed value is missing.

Measure	Description	Variable	Derivation / Comment	Imputation Approach if Missing Components
	
past 24 hours Refer to Section 6.2.2 for details on how to calculate the weekly score which will be used in the continuous analysis.
	
Pain-free days (Skin pain NRS = 0)
	
Count of observed value = 0 for 28-day (4-week) intervals starting on the day of the first study drug administration. This will be calculated for the following visit intervals: baseline to Week 4, Week 4 to Week 8, Week 8 to Week 12 and Week 12 to Week 16. Thus, if Day 1 is defined as the day of first study drug administration, the baseline to Week 4 assessment is based on Day 1 to Day 28, Week 4 to Week 8 is based on Day 29 to Day 56, etc.
	
If patients do not have at least 16 non-missing assessments in each 4-week interval, the score is missing.


Atopic Dermatitis Sleep Scale (ADSS)
	
The Atopic Dermatitis Sleep Scale (ADSS) is a 3-item, patient-administered questionnaire developed to assess the impact of itch on sleep including difficulty falling asleep, frequency of waking, and difficulty getting back to sleep last night. Patient's rate their difficulty falling asleep and difficulty getting back to sleep, items 1 and 3, respectively, using a 5-point Likert-type scale with response options ranging from 0 "not at all" to 4 "very difficult." Patients report their frequency of waking last night, item 2, by selecting the number of times they woke up each night, ranging from 0 to 29 times. The ADSS is designed to be completed each day with respondents thinking about sleep "last night." Each item is scored individually.
	
 ▪ Item 1 score of ADSS ▪ Item 2 score of ADSS ▪ Item 3 score of ADSS ▪ Change from baseline in score of Item 1 of ADSS ▪ Change from baseline in score of Item 2 of ADSS ▪ Change from baseline in score of Item 3 of ADSS 	
Single items: Item 1, range 0 to 4; Item 2, range 0 to 29; Item 3, range 0 to 4. Refer to Section 6.2.2 on how to derive the visit score.
 
Change from baseline: observed ADSS item score – baseline ADSS item score
	
Refer to Section 6.2.2 on how to derive the weekly visit score.
 
Missing if baseline or observed value is missing.

Measure	Description	Variable	Derivation / Comment	Imputation Approach if Missing Components
Patient-Oriented Eczema Measure (POEM)	The POEM is a simple, 7-item, patient-administered scale that assesses disease severity in children and adults. Patients respond to questions about the frequency of 7 symptoms (itching, sleep disturbance, bleeding, weeping/oozing, cracking, flaking, and dryness/roughness) over the last week. Response categories include “No days,” “1-2 days,” “3-4 days,” “5-6 days,” and “Every day” with corresponding scores of 0, 1, 2, 3, and 4, respectively. Scores range from 0-28 with higher total scores indicating greater disease severity (Charman et al. 2004).	POEM score	POEM total score: sum of questions 1 to 7, Range 0 to 28.	If a single question is left unanswered, then that question is scored as 0. If more than one question is unanswered, then the tool is not scored. If more than one response is selected, then the response with the highest score is used.
		Change from baseline in POEM score	Change from baseline: observed POEM score – baseline POEM score	Missing if baseline or observed value is missing.
Patient Global Impression of Severity–Atopic Dermatitis (PGI-S-AD)	The Patient Global Impression of Severity–Atopic Dermatitis (PGI-S-AD) is a single-item question asking the patient how they would rate their overall AD symptoms over the past 24 hours. The 5 categories of responses range from “no symptoms” to “severe.”	PGI-S-AD score	Single item. Range 1 to 5. Refer to Section 6.2.2 on how to derive the visit score.	Refer to Section 6.2.2 on how to derive the visit score.
		Change from baseline in PGI-S-AD	Change from baseline: observed PGI-S-AD score – baseline PGI-S-AD score	Missing if baseline or observed value is missing.

Measure	Description	Variable	Derivation / Comment	Imputation Approach if Missing Components
Hospital Anxiety Depression Scale (HADS)	The Hospital Anxiety Depression Scale (HADS) is a 14-item self-assessment scale that determines the levels of anxiety and depression that a patient is experiencing over the past week. The HADS utilizes a 4-point Likert scale (eg, 0 to 3) for each question and is intended for ages 12 to 65 years (Zigmond and Snaith 1983; White et al. 1999). Scores for each domain (anxiety and depression) can range from 0 to 21, with higher scores indicating greater anxiety or depression (Zigmond and Snaith 1983; Snaith 2003).	HADS score for anxiety and depression domains	Anxiety domain score is sum of the seven anxiety questions, range 0 to 21; Depression domain score is sum of the seven depression questions, range 0 to 21.	N/A – partial assessments cannot be saved.
		Change from baseline in HADS domain	Change from baseline: observed HADS domain score – baseline HADS domain score	Missing if baseline or observed value is missing.
Dermatology Life Quality Index (DLQI)	The Dermatology Life Quality Index (DLQI) is a simple, patient-administered, 10-item, validated, quality-of-life questionnaire that covers 6 domains including symptoms and feelings, daily activities, leisure, work and school, personal relationships, and treatment. The recall period of this scale is over the “last week.” Response categories include “a little,” “a lot,” and “very much,” with corresponding scores of 1, 2, and 3, respectively, and “not at all,” or unanswered (“not relevant”) responses scored as 0. Scores range from 0-30 with higher scores indicating greater impairment of quality of life. A DLQI total score of 0 to 1 is considered as having no effect on a patient’s health-related QoL (Hongbo et al. 2005), and a 4-point change from baseline is considered as the minimal clinically	Symptoms and feelings domain	Sum of questions 1 and 2, range 0 to 6.	N/A – partial assessments cannot be saved.
		Daily activities domain	Sum of questions 3 and 4, range 0 to 6.	N/A – partial assessments cannot be saved.
		Leisure domain	Sum of questions 5 and 6, range 0 to 6.	N/A – partial assessments cannot be saved.
		Work and school domain	Sum of questions 7 and 7B (if it is answered), range 0 to 3. Responses of “yes” and “no” on Question 7 are given scores of 3 and 0 respectively. If Question 7 is answered “no” then Question 7b is answered with “a lot”, “a little”, “not at all” getting scores of 2, 1, 0 respectively.	N/A – partial assessments cannot be saved.
	Personal relationships domain	Sum of questions 8 and 9, range 0 to 6.	N/A – partial assessments cannot be saved.	

Measure	Description	Variable	Derivation / Comment	Imputation Approach if Missing Components
	important difference threshold (Khilji et al. 2002; Basra et al. 2015).	Treatment domain	Question 10, range 0 to 3.	N/A – partial assessments cannot be saved.
		DLQI total score	DLQI total score: sum of all six DLQI domain scores, range 0 to 30.	N/A – partial assessments cannot be saved.
		Change from baseline in DLQI	Change from baseline: observed DLQI score – baseline DLQI score	Missing if baseline or observed value is missing.
Work Productivity and Activity Impairment: Atopic Dermatitis (WPAI-AD)	The Work Productivity and Activity Impairment Questionnaire–Atopic Dermatitis (WPAI-AD) records impairment due to AD during the past 7 days. The WPAI-AD consists of 6 items grouped into 4 domains: absenteeism (work time missed), presenteeism (impairment at work/reduced on-the-job effectiveness), work productivity loss (overall work impairment/absenteeism plus presenteeism), and activity impairment. Scores are calculated as impairment percentages (Reilly et al. 1993), with higher scores indicating greater impairment and less productivity.	Employment status	Question (Q)1	Single item, missing if missing.
		Change in employment status	Employed at baseline and remained employed: Q1 = 1 at post-baseline visit and at baseline visit. Not employed at baseline and remain unemployed: Q1 = 0 at post-baseline visit and at baseline visit.	Missing if baseline or observed value is missing.
		Percentage of absenteeism	Percent work time missed due to problem: $(Q2/(Q2 + Q4))*100$	If Q2 or Q4 is missing, then missing.
		Change from baseline in absenteeism	Change from baseline: observed absenteeism – baseline absenteeism	Missing if baseline or observed value is missing.
		Percentage of presenteeism	Percent impairment (reduced productivity while at work) while working due to problem: $(Q5/10)*100$	If Q5 is missing, then missing.
		Change from baseline in presenteeism	Change from baseline: observed presenteeism – baseline absenteeism	Missing if baseline or observed value is missing.
		Overall work impairment	Percent overall work impairment (combines absenteeism and presenteeism) due to problem: $(Q2/(Q2+Q4) + [(1-Q2/(Q2+Q4))*(Q5/10)])*100$	If Q2, Q4, or Q5 is missing, then missing.

Measure	Description	Variable	Derivation / Comment	Imputation Approach if Missing Components
		Change from baseline in work impairment	Change from baseline: observed work impairment – baseline work impairment	Missing if baseline or observed value is missing.
		Percentage of impairment in activities	Percent activity impairment (performed outside of work) due to problem: $(Q6/10)*100$	If Q6 is missing, then missing.
		Change from baseline in impairment in activities	Change from baseline: observed impairment in activities – baseline impairment in activities	Missing if baseline or observed value is missing.
European Quality of Life–5 Dimensions–5 Levels (EQ-5D-5L)	The European Quality of Life–5 Dimensions–5 Levels (EQ-5D-5L) is a standardized measure of health status that provides a simple, generic measure of health for clinical and economic appraisal. The EQ-5D-5L consists of 2 components: a descriptive system of the respondent’s health and a rating of his or her current health state using a 0 to 100 mm VAS. The descriptive system comprises the following 5 dimensions: mobility, self-care, usual activities, pain/discomfort, and anxiety/depression. Each dimension has 5 levels: no problems, slight problems, moderate problems, severe problems, and extreme problems. The respondent is asked to indicate his or her health state by ticking (or placing a cross) in the box associated with the most appropriate statement in each of the 5 dimensions. It should be noted that the numerals 1 to 5 have no arithmetic properties and should not be used as an ordinal score. The VAS records the respondent’s self-rated health on a vertical VAS where the endpoints are	
 ▪ EQ-5D mobility ▪ EQ-5D self-care ▪ EQ-5D usual activities ▪ EQ-5D pain/discomfort ▪ EQ-5D anxiety/depression 	Five health profile dimensions, each dimension has 5 levels: 1 = no problems 2 = slight problems 3 = moderate problems 4 = severe problems 5 = extreme problems It should be noted that the numerals 1 to 5 have no arithmetic properties and should not be used as a primary score.	Each dimension is a single item, missing if missing.
		EQ-5D VAS	Single item. Range 0 to 100. 0 represents “worst health you can imagine” 100 represents “best health you can imagine”	Single item, missing if missing.
		Change from baseline in EQ-5D VAS	Change from baseline: observed EQ-5D VAS score – baseline EQ-5D VAS score	Missing if baseline or observed value is missing.
		EQ-5D-5L UK Population-based index score (health state index)	Derive EQ-5D-5L UK Population-based index score according to the link by using the UK algorithm to produce a patient-level index score between -0.59 and 1.0 (continuous variable).	N/A – partial assessments cannot be saved on the eCOA tablet.
		Change from baseline in EQ-5D-5L UK	Change from baseline: observed EQ-5D-5L UK score – baseline EQ-5D-5L UK	Missing if baseline or observed value is

Measure	Description	Variable	Derivation / Comment	Imputation Approach if Missing Components
	labeled “best imaginable health state” and “worst imaginable health state.” This information can be used as a quantitative measure of health outcome. The EQ-5D-5L health states, defined by the EQ-5D-5L descriptive system, may be converted into a single summary index by applying a formula that essentially attaches values (also called weights) to each of the levels in each dimension (Herdman et al. 2011; EuroQol Group 2015 [WWW]).	Population-based index score	score	missing.
		EQ-5D-5L US Population-based index score (health state index)	Derive EQ-5D-5L US Population-based index score according to the link by using the US algorithm to produce a patient-level index score between -0.11 and 1.0 (continuous variable).	N/A – partial assessments cannot be saved on the eCOA tablet.
		Change from baseline in EQ-5D-5L US Population-based index score	Change from baseline: observed EQ-5D-5L US score – baseline EQ-5D-5L US score	Missing if baseline or observed value is missing.
Nocturnal Sleep-Wake and Itch Patterns	An actigraphy device, a hypoallergenic device worn on the wrist, will be used to collect sleep-wake patterns and quantify nocturnal scratching events. Each patient will be dispensed 2 actigraphy devices. One will be worn on the wrist at all times and the other will be worn only during hours of sleep (one on each wrist). Analyses for sleep-wake patterns will include: total sleep time (min), wake after sleep onset (WASO) (min), and sleep efficiency (%). Analyses for nocturnal scratching will include: scratching events (#), scratching duration (s), scratching events per hour (#/h), scratching duration per hour (s/h), and time from first to last scratching event (h).	Sleep-wake and itch patterns: Sleep: 
 ▪ Total sleep time (min) ▪ Wake after sleep onset (WASO) (min) ▪ Sleep efficiency (%) Scratching: 
 ▪ Scratching events (#) ▪ Scratching duration (s) ▪ Scratching events per hour (#/h) ▪ Scratching duration per hour (s/h) ▪ Time from first to last scratching event (h) 	Time from first to last scratching event = Time of last scratching event – time of first scratching event. Otherwise, single items. Refer to Section 6.2.2 on how to derive the visit score.	Refer to Section 6.2.2 on how to derive the visit score.
		
 ▪ Change from baseline in sleep-wake and itch patterns 	Change from baseline: observed score – baseline score	Missing if baseline or observed value is missing.

Table JAHM.6.7. Description of Health Outcomes and Quality-of-Life Measures Analyses

Measure	Variable	Analysis Method (Section 6.2.3)	Population (Section 6.2.1)	Comparison/Time Point	Analysis Type
Itch Numeric Rating Scale (NRS)	
 Itch NRS score Change from baseline in Itch NRS score 	MMRM	ITT	Bari 4-mg or Bari 2-mg or Bari 1-mg vs PBO; Week 4, 16	Secondary Analysis
		ANCOVA using mLOCF	ITT	Bari 4-mg or Bari 2-mg or Bari 1-mg vs PBO; Week 4, 16	Sensitivity Analysis
		pMI	ITT	Bari 4-mg or Bari 2-mg or Bari 1-mg vs PBO; Week 4, 16	Sensitivity Analysis
	Percent change from baseline Itch score	MMRM	ITT	Bari 4-mg or Bari 2-mg or Bari 1-mg vs PBO; Week 1, 16	Secondary Analysis
		ANCOVA using mLOCF	ITT	Bari 4-mg or Bari 2-mg or Bari 1-mg vs PBO; Week 1, 16	Sensitivity Analysis
	Proportion of patients achieving a 4-point improvement in Itch NRS in subgroup of patients who had baseline Itch NRS ≥ 4	Logistic regression using NRI	ITT	Bari 4-mg or Bari 2-mg or Bari 1-mg vs PBO; Week 1, 2, 4, 16	Key Secondary Analysis
			PPS	Bari 4-mg or Bari 2-mg or Bari 1-mg vs PBO; Week 16	Sensitivity analysis
		Logistic regression using pMI and Tipping Point	ITT	Bari 4-mg or Bari 2-mg or Bari 1-mg vs PBO; Week 16	Sensitivity analysis
Number of Itch-free (Itch NRS = 0) Days	Descriptive statistics	ITT	No comparisons; Week 12 to 16	Exploratory Analysis	
Skin Pain Numeric Rating Scale (NRS)	
 Skin Pain NRS score Change from baseline in Skin Pain NRS score 	MMRM	ITT	Bari 4-mg or Bari 2-mg or Bari 1-mg vs PBO; Week 16	Key Secondary Analysis
			PPS	Bari 4-mg or Bari 2-mg or Bari 1-mg vs PBO; Week 16	Sensitivity analysis
		ANCOVA using mLOCF	ITT	Bari 4-mg or Bari 2-mg or Bari 1-mg vs PBO; Week 16	Sensitivity Analysis
		pMI	ITT	Bari 4-mg or Bari 2-mg or Bari 1-mg vs PBO; Week 16	Sensitivity analysis
	Number of Skin Pain-free (Skin pain NRS = 0) Days	Descriptive statistics	ITT	No comparisons; Week 12 to 16	Exploratory Analysis

Measure	Variable	Analysis Method (Section 6.2.3)	Population (Section 6.2.1)	Comparison/Time Point	Analysis Type
Atopic Dermatitis Sleep Scale (ADSS)	
 ADSS item scores Change from baseline in ADSS item scores 	MMRM	ITT	Bari 4-mg or Bari 2-mg or Bari 1-mg vs PBO; Week 1, 16	Key Secondary Analysis
			PPS	Bari 4-mg or Bari 2-mg or Bari 1-mg vs PBO; Week 16	Sensitivity analysis
		ANCOVA using mLOCF	ITT	Bari 4-mg or Bari 2-mg or Bari 1-mg vs PBO; Week 1, 16	Sensitivity Analysis
		pMI	ITT	Bari 4-mg or Bari 2-mg or Bari 1-mg vs PBO; Week 16	Sensitivity analysis
Patient-Oriented Eczema Measure (POEM)	
 POEM score Change from baseline in POEM score 	MMRM	ITT	Bari 4-mg or Bari 2-mg or Bari 1-mg vs PBO; Week 16	Secondary Analysis
		ANCOVA using mLOCF	ITT	Bari 4-mg or Bari 2-mg or Bari 1-mg vs PBO; Week 16	Sensitivity Analysis
Patient Global Impression of Severity–Atopic Dermatitis (PGI-S-AD)	
 PGI-S-AD score Change from baseline in PGI-S-AD score 	MMRM	ITT	Bari 4-mg or Bari 2-mg or Bari 1-mg vs PBO; Week 16	Secondary Analysis
		ANCOVA using mLOCF	ITT	Bari 4-mg or Bari 2-mg or Bari 1-mg vs PBO; Week 16	Sensitivity Analysis
Hospital Anxiety Depression Scale (HADS)	
 HADS domain scores Change from baseline in HADS domain 	MMRM	ITT	Bari 4-mg or Bari 2-mg or Bari 1-mg vs PBO; Week 16	Secondary Analysis
		ANCOVA using mLOCF	ITT	Bari 4-mg or Bari 2-mg or Bari 1-mg vs PBO; Week 16	Sensitivity Analysis
Dermatology Life Quality Index (DLQI)	
 DLQI total score Change from baseline in DLQI Observed and change from baseline in domain scores 
 -Symptoms and feelings -Daily activities -Leisure -Work and school -Personal relationships -Treatment 	MMRM	ITT	Bari 4-mg or Bari 2-mg or Bari 1-mg vs PBO; Week 16	Secondary Analysis
		ANCOVA using mLOCF	ITT	Bari 4-mg or Bari 2-mg or Bari 1-mg vs PBO; Week 16	Sensitivity Analysis

Measure	Variable	Analysis Method (Section 6.2.3)	Population (Section 6.2.1)	Comparison/Time Point	Analysis Type	
Work Productivity and Activity Impairment: Atopic Dermatitis (WPAI-AD)	Observed and Change from baseline in employment status	Descriptive statistics (observed)	ITT	No comparisons; Week 16	Secondary Analysis	
European Quality of Life–5 Dimensions–5 Levels (EQ-5D-5L)	Observed and Change from baseline in: 
 • absenteeism • presenteeism • overall work impairment • impairment in activities 	MMRM	ITT	Bari 4-mg or Bari 2-mg or Bari 1-mg vs PBO; Week 16	Secondary Analysis	
		ANCOVA using mLOCF	ITT	Bari 4-mg or Bari 2-mg or Bari 1-mg vs PBO; Week 16	Sensitivity Analysis	
Nocturnal Itch assessed by Actigraphy Device	Observed values in 
 • EQ-5D mobility • EQ-5D self-care • EQ-5D usual activities • EQ-5D pain/ discomfort • EQ-5D anxiety/ depression 	Logistic Regression using NRI	ITT	Bari 4-mg or Bari 2-mg or Bari 1-mg vs PBO; Week 16	Exploratory Analysis	
		Observed and Change from baseline in: 
 • EQ-5D VAS • EQ-5D-5L UK Population-based index score • EQ-5D-5L US Population-based index score 	MMRM	ITT	Bari 4-mg or Bari 2-mg or Bari 1-mg vs PBO; Week 16	Secondary Analysis
			ANCOVA using mLOCF	ITT	Bari 4-mg or Bari 2-mg or Bari 1-mg vs PBO; Week 16	Sensitivity Analysis
Nocturnal Sleep-Wake and Itch scores	Change from baseline in Nocturnal Sleep-Wake and Itch scores: 
 -Total sleep time (min) -Wake after sleep onset (WASO) (min) -Sleep efficiency (%) -Scratching events (#) -Scratching duration (s) -Scratching events per hour (#/h) -Scratching duration per hour (s/h) -Time from first to last scratching event (h) 	MMRM	ITT	Bari 4-mg or Bari 2-mg or Bari 1-mg vs PBO; Week 1, 4	Exploratory Analysis	
		ANCOVA using mLOCF	ITT	Bari 4-mg or Bari 2-mg or Bari 1-mg vs PBO; Week 1, 4	Sensitivity Analysis	

Abbreviations: ANCOVA = analysis of covariance; Bari = baricitinib; ITT = intent-to-treat; mLOCF = modified last observation carried forward; MMRM = mixed model repeated measures; NRI = nonresponder imputation; PBO = placebo; pMI=placebo multiple imputation; PPS = per protocol set.

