4.2.2. Other Secondary Objectives

These are prespecified objectives that will not be adjusted for multiplicity.

Objectives	Endpoints
To test the hypothesis that baricitinib 1-mg QD, 2-mg QD, or 4-mg QD is superior to placebo in the treatment of patients with moderate to severe AD.	
 • Proportion of patients achieving IGA of 0 or 1 with a ≥ 2-point improvement at Week 4
To compare the efficacy of baricitinib 1-mg QD, 2-mg QD, or 4-mg QD to placebo in AD during the 16-week double-blind placebo-controlled period as measured by physician-assessed signs and symptoms of AD.	
 • Proportion of patients achieving EASI50 at 16 weeks • Proportion of patients achieving IGA of 0 at 16 weeks • Mean change from baseline in SCORAD at 16 weeks • Proportion of patients achieving SCORAD90 at 16 weeks • Mean change from baseline in BSA affected at 16 weeks • Proportion of patients developing skin infections requiring antibiotic treatment by Week 16
To compare the efficacy of baricitinib 1-mg QD, 2-mg QD, or 4-mg QD to placebo in AD during the 16-week, double-blind, placebo-controlled treatment period as assessed by patient-reported outcome/QoL measures.	
 • Percent change from baseline in Itch NRS at 1 week and 16 weeks • Mean change from baseline in Itch NRS at 4 weeks and 16 weeks • Mean change from baseline in the total score of the POEM at 16 weeks • Mean change in the PGI-S-AD scores at 16 weeks • Mean change from baseline in HADS at 16 weeks • Mean change in the DLQI scores at 16 weeks • Mean change in the WPAI scores at 16 weeks • Mean change in the EQ-5D-5L scores at 16 weeks

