6.2.4. Derived Data

- Age (year), derived using first dose date as the reference start date and July 1st of birth year and truncated to a whole-year (integer) age. Patients whose derived age is less than 18 will have the required minimum age of 18 at informed confirmed; reporting for age, age groups, and lab ranges, however will be based on their derived age.
- Age group (<65, ≥65 years old)
- Age group (<65, ≥65 to <75, ≥75 to <85, ≥85 years old)
- Body mass index (BMI) (kg/m^2) = $\text{Weight (kg)} / ((\text{Height (cm)} / 100)^2)$
- BMI category (<25 kg/m^2 , ≥25 to <30 kg/m^2 , ≥30 kg/m^2)
- The duration of AD from diagnosis (years) = $[(\text{Date of informed consent} - \text{Date of AD diagnosis}) + 1] / 365.25$.
 - If year of onset is missing, duration of AD will be set as missing. Otherwise, unknown month will be taken as January, and unknown day will be taken as 01. The duration of AD will be rounded to 1 decimal place.
- Duration of AD (years) category (0 to <2 years, 2 to <5 years, 5 to <10 years, 10 to <20 years, ≥20 years)
- Diagnosis age (years), derived using diagnosis date as the reference start date and July 1st of birth year and truncated to a whole-integer age.
- Diagnosis age group (<18, ≥18 to <50, ≥50 years old)
- Change from baseline = postbaseline measurement at Visit x – baseline measurement.
 - If a baseline value is missing, it will not be imputed and the change from baseline will not be calculated.
- Percent change from baseline at Visit x:
 $((\text{Post-baseline measurement at Visit x} - \text{Baseline measurement}) / \text{Baseline measurement}) * 100$.
 - If a baseline value is missing, it will not be imputed and percent change from baseline will not be calculated.
- Weight (kg) = weight (lbs) * 0.454.
- Weight category (<60 kg, ≥60 to <100 kg, ≥100 kg)
- Height (cm) = height (in) * 2.54.
- Cyclosporine inadequate efficacy (yes, no)
 - Set **yes** if the reason for discontinuation is inadequate response.
- Cyclosporine intolerance (yes, no)

- Set **yes** if the reasons for discontinuation are: intolerance to medication or contraindication (Physician indicated cyclosporine was used and a contraindication was noted).
- Cyclosporine contraindication [ineligible] (yes, no)
 - Set to **yes** if cyclosporine never used because of a contraindication
- Cyclosporine inadvisable (yes, no)
 - Set to **yes** if the following reasons were selected for either not using the medication or discontinuing the medication:

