6.3. Covariate Adjustment

The randomization to treatment groups at Week 0 (Visit 2) is stratified by disease severity (IGA) and geographic region as described in Section 5.1. Unless otherwise specified, the statistical analysis models will adjust for these stratification variables. The covariates used in the logistic model for categorical data will include the parameter value at baseline. The covariates used in the ANCOVA model for continuous data will include the parameter value at baseline. Inclusion of baseline in the model ensures treatment LSM are estimated at the same baseline value. When an MMRM analysis is performed, baseline value and baseline-by-visit interactions will be included as covariates.

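### The WPAI-AD presenteeism change score subtracts baseline absenteeism, so the within-arm mean changes computed as written are wrong and can change sign

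*SAP*

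**What the plan says.** Section 4.2.2 lists "Mean change in the WPAI scores at 16 weeks" among the secondary endpoints that are not adjusted for multiplicity. Table JAHM.6.6 in Section 6.12 gives the derivations. Presenteeism is (Q5/10)*100 and absenteeism is (Q2/(Q2+Q4))*100. The four WPAI-AD percentage scores then have these change rules:

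- Absenteeism: "Change from baseline: observed absenteeism – baseline absenteeism"
- Presenteeism: "Change from baseline: observed presenteeism – baseline absenteeism"
- Overall work impairment: "Change from baseline: observed work impairment – baseline work impairment"
- Activity impairment: "Change from baseline: observed impairment in activities – baseline impairment in activities"

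The general rule in Section 6.2.4 is "Change from baseline = postbaseline measurement at Visit x – baseline measurement". Section 6.3 adds, for the models: "The covariates used in the ANCOVA model for continuous data will include the parameter value at baseline". Table JAHM.6.7 plans MMRM, with ANCOVA on mLOCF data as sensitivity analysis, at Week 16 for "Observed and Change from baseline in" each of the four scores, presenteeism included.

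**The concern.** The presenteeism row is the only one of the four that does not subtract its own baseline. What it defines is not a change in anything: it is the Week 16 value of one score minus the baseline value of another, built from different questionnaire items. Table JAHM.6.6 is the variable-specific derivation that a programmer would work from, and the SAP does not say whether it or Section 6.2.4 takes precedence.

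If the row is coded literally, the mean presenteeism change reported for each arm is wrong and may show worsening where patients improved. On the natural reading of the formula, whether a change score is missing would also depend on baseline Q2 and Q4, not on baseline Q5. The missing-data entry in that row does not name the baseline it means, so this second effect is less certain than the first.

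**Working it through.** The SAP states no figure for this score, so there is none to reproduce. The check is algebra, followed by examples.

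**Algebra.** Let P0 and P16 be presenteeism at baseline and Week 16, and A0 absenteeism at baseline.

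- Correct change = P16 − P0
- Change as written = P16 − A0
- Error = (P16 − A0) − (P16 − P0) = P0 − A0

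The error is zero only when P0 = A0. A true improvement appears as a worsening whenever P16 exceeds A0.

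**One patient, from the SAP's formulas alone.** Take Q2 = 0 and Q4 > 0 at baseline, with Q5 falling from 6 to 3.

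- P0 = (6/10)*100 = 60; P16 = (3/10)*100 = 30; A0 = 0/(0+Q4)*100 = 0
- Correct: 30 − 60 = −30
- As written: 30 − 0 = +30

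For every patient with no missed work at baseline, the written change equals the Week 16 score. It cannot be negative, so improvement cannot register.

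**Dependence on baseline absenteeism.** With Q5 falling from 5 to 3 (50 to 30), the correct change is −20 throughout:

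| A0 | As written | Error |
|---|---|---|
| 5 | +25 | +45 |
| 10 | +20 | +40 |
| 40 | −10 | +10 |
| 50 | −20 | 0 |
| 70 | −40 | −20 |

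The error can therefore go either way: when baseline absenteeism exceeds baseline presenteeism, improvement is overstated.

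**Group means (assumed; the SAP gives none).** Take mean P0 35 to 50, mean A0 5 to 15 and mean P16 25 to 30.

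- Correct: from 25 − 50 = −25 to 30 − 35 = −5
- As written: from 25 − 15 = +10 to 30 − 5 = +25
- Error: from 35 − 15 = +20 to 50 − 5 = +45

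Over a wider assumed grid (P0 30 to 60, A0 5 to 40, true change −5 to −25), the written mean runs from 60 − 5 − 5 = +50 to 30 − 40 − 25 = −35. The sign does not always flip: P0 = 30, A0 = 20 and a true change of −15 give −5.

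**Difference between arms.** Under randomization P0 − A0 has the same expectation in every arm, so it cancels. In 4,000 simulated trials (240 placebo, 120 active, true difference −10, assumed score distributions):

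| Derivation | Mean change, placebo | Mean change, active | Adjusted difference |
|---|---|---|---|
| Correct | −7.2 | −17.2 | −10.0 |
| As written | +24.1 | +14.1 | −10.0 |

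Both within-arm signs flip and the difference survives. The standard error was 2.24 with the correct score. With the written one it was 2.73 adjusting for P0 and 2.46 adjusting for A0. That increase depends on the assumed spreads and correlations, so no general conclusion on precision follows.

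**The case against.** The strongest reply is that this is a plain copying slip from the absenteeism row. The row's name, Section 6.2.4, Section 6.3 and the three sibling rows all point to baseline presenteeism, and no rival reading is plausible. A programmer would probably query it or correct it, and nothing shows that any result would be produced from the literal rule. This is fair as to likelihood, but it does not make the row correct.

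The second reply is that the treatment comparison is largely protected. Table JAHM.6.7 also plans the analysis of the observed presenteeism score. With baseline presenteeism as covariate and the same patients, that model gives the same difference between arms as a correctly derived change score: in ANCOVA always, and in the MMRM because it includes baseline-by-visit. This stands. Section 6.2.3 bases inference on differences from placebo, so what remains exposed is mainly the display of within-arm change.

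Third, the score is one of four WPAI-AD percentage scores in an endpoint outside the testing procedure of Section 6.6, and the group-mean ranges are assumptions. Both are true. The point rests on the algebra and the single-patient example, which need no assumed means.

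**Conclusion.** The concern holds. The derivation is wrong as written and contradicts the rest of the SAP. Coded literally, it shifts each arm's mean presenteeism change by mean P0 minus mean A0. That is +20 to +45 points under the first set of assumed means, enough there to turn an improvement into an apparent worsening in every arm.

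The damage is confined to within-arm change for one domain of an unadjusted secondary endpoint. The difference between arms stays unbiased in expectation, and the primary endpoint, key secondary endpoints, sample size and alpha allocation are untouched. It should be fixed because the row feeds a planned analysis and the correction is unambiguous, not because it threatens the trial's main conclusions.

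**What to change.** In the presenteeism change row of Table JAHM.6.6, replace absenteeism with presenteeism as the baseline term, so that the rule is observed presenteeism minus baseline presenteeism. Then confirm in the analysis dataset specification and programs that the derived change, its missing-data rule and the baseline covariate in both the MMRM and the ANCOVA use baseline presenteeism. The cost is one word in the SAP and a short programming check.
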